#### A. All patients

- i] Proportion of patients having a reduction in CVVS score on Day 7 compared to Day 0
- ii] Change in the CVVS score from Day 0 to Day 7
- iii] Proportion of patients having a reduction in the sum of the 3 vulvovaginal symptoms scores (itching, burning, and irritation) on Day 4 and Day 7, compared to Day 0
- iv] Change in the sum of the 3 vulvovaginal symptoms scores (itching, burning, and irritation) from Day 0 to Day 4 and Day 7
- v] Proportion of patients receiving prolonged treatment
- vi] Usability, measured by patient questionnaire

The endpoints i], iii], v], and the first 4 questions in endpoint vi] are binary variables.

The endpoints ii], iv], and the 5th question in vi] are considered as continuous variables.

#### B. For patients not receiving prolonged treatment

- vii] Recurrence rate on Day 14 and Day 35, defined as the proportion of patients clinically cured on Day 7 and thereafter responding "yes" to a yes/no question from the patient questionnaire on whether the symptoms have recurred

The endpoint vii] constitute binary variables.

#### C. For patients receiving prolonged treatment

- viii] Clinical cure rate on Day 14, defined as the absence of signs and symptoms of VVC in terms of having a CVVS score equal to or below 3

- ix] Proportion of patients having a reduction in CVVS score on Day 14 compared to Day 0
- x] Change in the CVVS score from Day 0 to Day 14
- xi] Proportion of patients having a reduction in the sum of the 3 vulvovaginal symptoms scores (itching, burning, and irritation) on Day 11, Day 14, Day 21, and Day 42, compared to Day 0
- xii] Change in the sum of the 3 vulvovaginal symptoms scores (itching, burning, and irritation) from Day 0 to Day 11, Day 14, Day 21, and Day 42
- xiii] Recurrence rate on Day 21, and Day 42, defined as the proportion of patients clinically cured on Day 14 and thereafter responding “yes” to a yes/no question from the patient questionnaire on whether the symptoms have recurred
- xiv] Proportion of patients receiving prescription for fluconazole on Day 14

The endpoints viii], ix], xi], xiii], and xiv] are binary variables.

The endpoints x] and xii] are considered as continuous variables.

In connection to the endpoints described above, the underlying variables listed below not constituting endpoints (denoted as “other related variables” in the CIP), will be presented descriptively.

- CVVS score (can take integer values in the interval 0-18)
- Vulvovaginal signs: erythema (can take integer values in the interval 0-3)
- Vulvovaginal signs: edema (can take integer values in the interval 0-3)
- Vulvovaginal signs: excoriation (can take integer values in the interval 0-3)
- Sum of all vulvovaginal signs score (can take integer values in the interval 0-9)
- Vulvovaginal symptoms: itching (can take integer values in the interval 0-3)
- Vulvovaginal symptoms: burning (can take integer values in the interval 0-3)
- Vulvovaginal symptoms: irritation (can take integer values in the interval 0-3)
- Sum of all vulvovaginal symptoms score (can take integer values in the interval 0-9)

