3.2.1 Risks and Benefits

The investigational device, Gedea Pessary has been evaluated in accordance with ISO 10993 (Biological Evaluation of Medical Devices). The evaluation included: cytotoxicity testing (Direct cell contact test, ISO 10993-5); *in vivo* irritation (Vaginal acute irritation; ISO 10993-10); and sensitization (local lymph node assay, ISO 10993-10). The *in vitro* cytotoxicity test, classified the test item as slight to moderate cytotoxic (scale 1–2 on a 3-grade scale); the *in vivo* irritation test as well as the *in vivo* sensitization test showed no signs of irritation, necrosis or sensitization after treatment with Gedea Pessary.

The vaginal pessary may, in similarity with other vaginally administered products, cause temporary minor discomfort at insertion. The vaginal sampling procedures are similar to sampling procedures used in clinical practice are unlikely to cause any major inconvenience to patients. In the Laccure pessary study,⁴⁴ there were no SAEs and vaginal itching was the most common AE.

There is a risk that patients will have no clinical benefit from the investigational device. This may cause patients to experience symptoms including vaginal itching, burning or soreness, pain during sexual intercourse, pain or discomfort when urinating, or abnormal vaginal discharge longer than necessary.^{1,45} However, fluconazole will be offered on Day 14 if any symptoms should still be present, thus avoiding any risk associated with long-term untreated VVC.

^a And on Day(s) 7, 9, 11, and 13 if receiving prolonged treatment

Protocol Version 3.0, 24Oct2018

LINK Medical Research | Protocol template

Version 2.0 | Effective date 17Apr2018

Subjects included in the study must refrain from using other intravaginal products, thus mitigating the risk of interactions with concomitant vaginally-administered products. The investigational device acts locally on the vaginal mucosa and most likely will most likely not affect any concomitant systemic treatment.

Taken together, as the anticipated levels of discomfort are transient and mild, and that risks associated with VVC are avoidable, the use of the investigational product appears to offer clinical benefits at a reasonable risk level.

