3.5.10 Day 14 (+2 Days); Follow-up Visit

Applicable to patients receiving prolonged treatment

Patients receiving prolonged treatment at Day 7 due to still-present VVC symptoms will visit the site on Day 14 to have gynecological examination performed and vulvovaginal signs (erythema, edema, or excoriation) and symptoms (itching, burning, or irritation) assessed by the Investigator or an authorized designee. Patients will receive fluconazole should symptoms still be present.

Vaginal samples will be examined by microscope to reveal yeast forms (hyphae or pseudohyphae) or budding yeast and secretion samples collected by swab to be used for sequencing analysis of the vaginal microbiome.

In addition, patients will be asked questions from the patient questionnaire to assess usability and AEs, if any.

Procedures performed:

- Gynecological examination by Investigator or authorized designee evaluating signs (erythema, edema, or excoriation) and symptoms (itching, burning, or irritation) of VVC according to the scoring scale
- Fungal KOH microscope assessment
- Vaginal swab for sequencing
- Recording of:
 - concomitant medications,
 - adverse events, and
 - usability

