3.5.11 Day 21 (± 2 Days); Follow-up Telephone Contact

Applicable to patients receiving prolonged treatment

Patients receiving prolonged treatment on Day 7 will be contacted by the Clinical Trial Unit by telephone on Day 21. Patients will be asked questions from the patient questionnaire pertaining to VVC symptoms (itching, burning, or irritation). Questions on concomitant medications, recurrence, and AEs, if any, will also be asked.

Procedures performed:

- Vulvovaginal candidiasis recurrence
- Symptoms (itching, burning, or irritation) of VVC evaluated by patients according to the scoring scale
- Recording of:
 - concomitant medications, and
 - adverse events

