3.5.13 Day 42 (± 2 Days); Follow-up Telephone Contact

Applicable to patients receiving prolonged treatment

Patients receiving prolonged treatment will be contacted over telephone by the Clinical Trial Unit on Day 42 and asked questions from the patient questionnaire relating to VVC symptoms (itching, burning, or irritation). Patients will also be asked questions on recurrence, concomitant medications, and AEs, if any. Patients will collect vaginal samples by self-swab to be sent by post to laboratory for sequencing.

Procedures performed:

- Vulvovaginal candidiasis recurrence
- Symptoms (itching, burning, or irritation) of VVC evaluated by patients according to the scoring scale
- Vaginal swab for sequencing
- Recording of:
 - concomitant medications, and
 - adverse events

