#### 3.2 Secondary objectives

To further investigate the clinical performance of the investigational product.

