## Figure 1 Study Flow Chart

VVS = Vulvovaginal Symptoms, VS = Vaginal Swab, CVVS = Composite Vulvovaginal Signs and Symptoms

**Patients not receiving prolonged treatment** applies to patients cured at Day 7. If not cured, the flow chart **patients receiving prolonged treatment** applies. Patients will here receive fluconazole if not cured at Day 14. Adverse events will be assessed throughout the study

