### 7.2.1 *Full analysis set*

Full Analysis Set (FAS): This is the primary population and comprises all patients entering the study and having received at least 1 dose of study treatment. Analyses of clinical performance will be performed against this population.

In addition to this, two sub-populations based on this FAS will be formed: “FAS (For patients not receiving prolonged treatment)”, and “FAS (For patients receiving prolonged treatment)”.

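### Late symptom endpoints xi and xii (Days 21 and 42) include scores taken after Day 14 fluconazole, and endpoint xiv is derived as something other than its name

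*SAP*

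**What the plan says.** The secondary objective concerns the product itself: "To further investigate the clinical performance of the investigational product" (SAP 3.2). Endpoints xi (proportion with a reduction) and xii (mean change) use the sum of itching, burning and irritation: "itching, burning, and irritation) on Day 11, Day 14, Day 21, and Day 42, compared to Day 0" in xi, with the same four days in xii. The population is the sub-population "FAS (For patients receiving prolonged treatment") in SAP 7.2.1, with no exclusion for rescue.

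Fluconazole enters this group at Day 14, but the trigger is worded in several ways:
- Flow chart (Figure 1): "Patients will here receive fluconazole if not cured at Day 14".
- Protocol 3.2.1: "fluconazole will be offered on Day 14 if any symptoms should still be present".
- Protocol 3.5.10: "Patients will receive fluconazole should symptoms still be present".
- Protocol 5.2.1: a prescription where it is judged necessary for symptom relief.

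Later scoring makes no exception for rescued patients: "Patients receiving prolonged treatment on Day 7 will be contacted by the Clinical Trial Unit by telephone on Day 21" (Protocol 3.5.11) and "Patients receiving prolonged treatment will be contacted over telephone by the Clinical Trial Unit on Day 42" (Protocol 3.5.13). Both calls ask for symptom scores, as do Protocol Table 3 and Appendix 1. SAP 7.1.5 uses observed data without imputation, and SAP 8.7 treats any change below zero as a reduction.

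Endpoint xiv is named as the proportion prescribed fluconazole on Day 14 (Protocol 2.2; SAP 3.2.1 and 7.9.2 C). SAP 8.10 derives it from concomitant-medication data as rescue treatment used, starting on or after Day 14, with no upper limit. SAP 7.11 does not list this among the changes.

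**The concern.** Rescue at Day 14 is part of the design, so symptom scores after an antifungal are foreseeable. A patient who did not respond to eight pessaries and then improved on fluconazole would count as reduced in xi and would pull the xii mean down, in tables that serve a pessary-performance objective. The SAP identifies and lists rescue use (7.7, 8.10) but does not link it to xi or xii. The per-protocol sets in SAP 7.2.2 are built for the primary endpoint and for recurrence, so they do not separate the two treatments here either.

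For xiv, both the event (use, not prescription) and the timing (open-ended, not Day 14) differ from the name. A prescription that is never taken is missed. Later rescue-coded use, for example at a withdrawal after Day 14 (allowed by Protocol 5.2.1), is counted. Protocol 9.1 asks for changes to specified analyses to be documented and justified in the SAP.

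**Working it through.** **Inputs.** The plan gives no figure for this point. Its only design calculation is 22 evaluable patients for the Day 7 cure rate. It reproduces by the normal approximation: [(1.645·√(0.4·0.6) + 1.282·√(0.7·0.3))/0.3]² = 21.56, rounded up to 22. Only its 70% cure assumption and the planned 24 patients are used below. The number rescued and the score changes are not in the documents, so they are assumptions.

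**Size of the prolonged-treatment group.** 24 × (1 − 0.70) = 7.2, taken as 7. If 80% or 60% are cured at Day 7, 24 × 0.20 = 4.8 (about 5) or 24 × 0.40 = 9.6 (about 10).

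**Endpoint xi.** Let n be the group size, r the number rescued and a the number of rescued patients already reduced at Day 14. If all rescued patients are reduced after fluconazole, the most that rescue can add is (r − a)/n. With n = 7 and r = 2:
- a = 2: 0/7 = 0 points
- a = 1: 1/7 = 14 points
- a = 0: 2/7 = 29 points

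With a = 0, the ceiling for r = 1, 2, 3, 4 of 7 is 14, 29, 43 and 57 points. For r = 2 it is 2/5 = 40 points with 5 patients and 2/10 = 20 points with 10. All are upper bounds, because a 1-point fall by Day 14 already makes a patient reduced.

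**xi and xii on one set of patients.** Assume 5 patients not rescued, at −4 throughout, and 2 rescued, at −5 after fluconazole.

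| Rescued patients at Day 14 | xi Day 14 | xi Day 21 | xii Day 14 | xii Day 21 |
|---|---|---|---|---|
| Case A: −2 each | 7/7 | 7/7 | (5·(−4) + 2·(−2))/7 = −3.43 | (5·(−4) + 2·(−5))/7 = −4.29 |
| Case B: 0 each | 5/7 | 7/7 | (5·(−4) + 2·0)/7 = −2.86 | −4.29 |

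In case A, xi does not move and xii shifts by −0.86. In case B, xi rises by 29 points and xii shifts by −1.43. The two-sided Clopper-Pearson 95% limits that SAP 7.9.2 specifies are 29.0 to 96.3% for 5/7 and 59.0 to 100% for 7/7. The intervals overlap widely, so the matter is what the estimate means, not its precision.

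**Endpoint xiv.** One patient counted wrongly moves it by 1/7 = 14 points (1/10 = 10 to 1/5 = 20).

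**The case against.** The strongest reply is that the plan does have a rule in effect. The full analysis set, observed data and scoring of every prolonged-treatment patient together mean that scores after rescue are included, whatever the rescue. That is right, and a claim that the plan has no rule at all would go too far. What stands is that this include-all approach is unlabelled, while the endpoints are presented as product performance.

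It is also fair that these are secondary endpoints in a feasibility study. The binary ones carry no hypothesis test, the Day 14 results for the same patients are reported, and listings let a reader partly separate the effects. The score changes above are invented, and in case A the effect on xi is zero. For xiv, an open start date accommodates the visit window of up to two days and delayed intake. Misclassified patients should be few, because Protocol 5.7 prohibits other antifungals. This limits the weight of the point. It does not supply a label for the late totals or an end to the xiv window.

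Two stronger readings may tempt a reader:

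- **Safety-only follow-up after rescue.** Protocol 3.6 says that patients given fluconazole on Day 14 are followed for safety, from which one might infer that they have no late symptom scores. The sentence stands under early withdrawal and does not cancel the Day 21 and Day 42 scoring. Even on that reading, the xi denominator is open: SAP 7.1.1 keeps missing patients in by default, whereas SAP 7.1.5 points to observed data. No firm figure follows.
- **Distortion of recurrence (xiii).** Under the Protocol 3.2.1 or 3.5.10 wording, a patient with a CVVS score of 3 or less but remaining symptoms could be rescued and still count as cured on Day 14. But SAP 8.8 defines recurrence from Day 7 cure, whereas xiii uses Day 14 cure. With the derivation itself unsettled, the size of any effect on xiii cannot be stated.

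**Conclusion.** Both parts hold. As written, xi and xii at Days 21 and 42 mix the pessary with Day 14 fluconazole, and xiv does not measure the event in its name. With an assumed 7 prolonged-treatment patients and 2 rescued, the effect on xi lies between 0 and 29 points, depending on whether the rescued patients had already improved at Day 14. The assumed score changes shift the xii mean by 0.9 to 1.4 points. One misclassified patient moves xiv by about 14 points (10 to 20 over the plausible group sizes).

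The documents do not support extending this to the primary Day 7 cure rate or to the Day 11 and Day 14 results, none of which is affected by Day 14 rescue. Nor do they show that late results must be inflated: the xi figures are ceilings. The point is minor to moderate and worth correcting.

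**What to change.** **SAP 7.9.2.** Label the Day 21 and Day 42 totals for xi and xii as regardless of rescue. Beside them, show patients with and without fluconazole before that contact, with the number in each row. Add a note that the row without fluconazole is selected on Day 14 response and must not be read alone as the pessary effect. For xi, add a version with rescued patients counted as not reduced, labelled as a lower-bound sensitivity figure. It also removes reductions reached on the pessary: in case A it gives 5/7 although all 7 had improved by Day 14.

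**SAP 8.10 and 7.11.** Derive xiv from the Day 14 prescription if that is recorded, which the documents do not state. Otherwise relabel it as rescue use from Day 14 onward, with use linked to the Day 14 visit and later use on separate lines. List the change in 7.11.

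**Reconcile.** The passages on when fluconazole is given (Protocol 3.2.1, 3.5.10, 5.2.1 and the flow chart) must be brought into agreement, as must those on follow-up afterwards (Protocol 3.5.11, 3.5.13 and 3.6).

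**Cost.** SAP wording and a few table rows. Rescue use is already recorded in the eCRF (Protocol 5.2.1) and its dates are listed (SAP 8.10). The rows will be very small, and the late figures may look less favourable.

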### 7.9.3 *Exploratory endpoints*

#### All patients

- xv] Effect on vaginal microbiome on Day 0 and Day 7
- xvi] Vaginal pH on Day 7

#### For patients not receiving prolonged treatment

- xvii] Effect on vaginal microbiome on Day 35

#### For patients receiving prolonged treatment

- xviii] Effect on vaginal microbiome on Day 14 and Day 42

The endpoints related to vaginal microbiome (endpoints xv], xvii] and xviii]) will be presented after study completion.

Vaginal pH, i.e. endpoint xvi] is considered as a continuous variable and will be presented descriptively.

### 7.9.4 *Sensitivity analyses of the primary clinical performance endpoint*

In addition to what is stated in the CIP, a sensitivity analysis is added in the analysis of the primary clinical performance endpoint. In this, patients responding “Negative” to the eCRF variable “Vaginal swab culture result”, [see Section 7.10.3](#) below, will be excluded.

## 7.10 Safety evaluation

All evaluations of safety data will be performed on the full analysis set.

### 7.10.1 Extent of exposure

See [Section 7.8](#) above. Furthermore, as a measure of investigational product *in vivo* duration, patients' vaginal pH will be assessed on Day(s) 0 and 7. Vaginal pH lower at follow-up visits compared to Day 0 indicate appropriate release duration. Summary statistics on the vaginal pH will be presented.

### 7.10.2 Adverse Events

Adverse events will be coded according to MedDRA.

Only treatment-emergent adverse events, i.e. adverse events starting after administration of first dose of study treatment, will be presented as described below. Any adverse events reported to start before administration of first dose of study treatment will be listed separately. In the remainder of this section, the term "adverse event" should be interpreted as "treatment-emergent adverse event".

An overview of all adverse events will be presented, including the number and percentage of patients with at least one, and the total number, of the following:

- Adverse events.
- Serious adverse events.
- Adverse events leading to withdrawal of the investigational product.
- Fatal adverse events.
- Adverse events, broken down by severity (intensity).
- Adverse events, broken down by causality assessment (relationship).

The International Organization for Standardization (ISO) terms ADE, SADE, ASADE, USADE introduced in the CIP constitute adverse events where relationship to investigational device or study procedure is indicated. The classification of an untoward medical event as USADE or ASADE will be done retrospectively. The event will initially be captured as a serious adverse event.

The incidence of adverse events will be presented by system organ class and preferred term. For each system organ class and preferred term, the total number of adverse events as well as the number and percentage of patients with at least one adverse event in that system organ class or preferred term will be presented. The incidence of serious adverse events will be presented in the same way.

Separate tables for the incidence of adverse events broken down by severity and the incidence of adverse events broken down by causality assessment will also be presented by system organ class and preferred term.

There will also be tables on the most frequently reported adverse events, on system organ class level and on preferred term level. The decision on the frequency cut-off for these tables will be taken during the analysis of the adverse events data in consultation with the author of the clinical study report

and could be influenced by factors such as the overall number of adverse events, study design, and the nature of the indication. The frequency cut-off should be mentioned in a table note.

Device deficiencies, as captured by the Device Event CRF module, will be presented in data listings only. If any device event is considered as also constituting an adverse event, it should be reported also as an adverse event.

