7.3 Untoward Medical Events / Adverse Events

The definitions are the definitions in the current version of the ISO 14155. The categorization will adhere to the following table in ISO 14155;

Table 4 Untoward Medical Events / Adverse Events Categorization

ADVERSE EVENTS	Non-device related	Device-or-procedure related	
Non-serious	Adverse Event (AE) ^a (3.2)	Adverse Device Effect (ADE) (3.1)	
Serious	Serious Adverse Event (SAE) ^b (3.37)	Serious Adverse Device Effect (SADE) (3.36)	
		Anticipated	Unanticipated
		Anticipated Serious Adverse Device Effect (ASADE) (3.42, Note)	Unanticipated Serious Adverse Device Effect (USADE) (3.42)

References in parentheses refer to sections in the standard ISO 14155:2011

^a Includes all categories.

^b Includes all categories that are serious

Adverse events are any untoward medical occurrence, unintended disease or injury, or untoward clinical signs (including abnormal laboratory findings) in subjects, users or other persons, whether or not related to the investigational medical device.

The AE may be directly related to the use of an investigational medical device and are then called an adverse device effect (ADE). This includes events due to insufficient or incomplete instructions, use, implantation, or dysfunction of the tested product. Misuse and errors while using the product are also included in the ADE definition.

The following events are not considered untoward medical events / AEs:

- Medical interventions planned before study initiation given that the status of the participant has not worsened since signing the consent form or the intervention has had to be done at an earlier date.
- All conditions or diseases known at the time when the subject signs the informed consent form, are not considered untoward medical events / AEs. These will be registered in the medical history CRF page.

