7.4 Serious Untoward Medical Events / Serious Adverse Events

An SAE is an AE that lead to serious deterioration in the health of the subject, that resulted in one or more of the below:

- death, or
- an immediately life-threatening illness or injury, or
- a permanent impairment of a body structure or a body function, or
- in-patient or prolonged hospitalization, or
- requires intervention to prevent life-threatening illness, or injury or permanent impairment to a body structure or a body function, or
- led to fetal distress, fetal death or a congenital abnormality or birth defect.

NOTE: Planned hospitalization for a pre-existing condition, or a procedure required by the current CIP, without serious deterioration in health, is not considered an SAE.

A serious adverse device effect (SADE) is an ADE that has resulted in any of the consequences characteristic of a SAE.

An unanticipated serious adverse device effect (USADE) is a SADE, which by its nature, incidence, severity, or outcome has not been identified in the current version of the risk analysis report

NOTE: Anticipated serious adverse device effect (ASADE) is an effect, which by its nature, incidence, severity, or outcome has been identified in the risk analysis report. The classification of an untoward medical event as USADE or ASADE will be done retrospectively. The event will initially be captured as an SAE.

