^a When the event is not a known side effect of the product category the device belongs to or of similar devices and procedures, generally is considered "not related". Yet, the unexpected effect shall not be excluded from evaluation and reporting.

^b If an investigational device gives an incorrect diagnosis, the patient might, for example, receive an unnecessary treatment and incur all the risks that accompany that treatment, or might be incorrectly diagnosed with a serious disease. In other cases, the patient might not receive an effective treatment (thereby missing out on the benefits that treatment would confer), or might not be diagnosed with the correct disease or condition.

assessed or no information has been obtained should also be classified as possible.

Probable: The relationship with the use of the investigational device seems relevant and/or the event cannot reasonably explained by another cause, but additional information may be obtained.

Causal Relationship: The serious event is associated with the investigational device or with procedures beyond reasonable doubt when:

- the event is a known side effect of the product category the device belongs to or of similar devices and procedures;
- the event has a temporal relationship with investigational device use/application or procedures;
- the event involves a body-site or organ that
 - the investigational device or procedures are applied to;
 - the investigational device or procedures have an effect on;
- the serious event follows a known response pattern to the medical device (if the response pattern is previously known);
- the discontinuation of medical device application (or reduction of the level of activation/exposure) and reintroduction of its use (or increase of the level of activation/exposure), impact on the serious event (when clinically feasible);
- other possible causes (e.g. an underlying or concurrent illness/ clinical condition or/and an effect of another device, drug or treatment) have been adequately ruled out;
- harm to the subject is due to error in use;
- the event depends on a false result given by the investigational device used for diagnosis^a, when applicable;
- In order to establish the relatedness, not all the criteria listed above might be met at the same time, depending on the type of device/procedures and the serious event.

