9.2.3.2 Adverse Events

The AEs will be presented descriptively by means of frequency and percentages to evaluate both the rate of incidence and event occurrence among the different treatment groups. The descriptive tables will be presented with respect to intensity, seriousness, and relationship to the treatment.

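### The causality scale mixes relationship to the device with relationship to study procedures, so an event caused by an examination or swab can be tabulated as treatment-related

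*SAP*

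**What the plan says.** **Rating.** Protocol 7.5.2 asks the investigator to judge how each event relates to the device and gives five levels. The middle levels speak of the device only; for *Probable* the text is "The relationship with the use of the investigational device seems relevant". The two end levels are wider. *Not Related* applies when a link to the device or to procedures can be excluded. *Causal Relationship* reads "The serious event is associated with the investigational device or with procedures beyond reasonable doubt when", followed by criteria that include timing relative to procedures and a body site to which procedures are applied.

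**Classification.** In protocol 7.3 the running text defines an adverse device effect (ADE) by its relation to use of the device, and all its examples concern the product. Table 4 in the same section places ADEs under "Device-or-procedure related". The protocol gives the table precedence: "The categorization will adhere to the following table in ISO 14155". Protocol 7.4 carries the ADE definition over to serious events: "A serious adverse device effect (SADE) is an ADE that has resulted in any of the consequences characteristic of a SAE". SAP 7.10.2 follows the table: ADE, SADE, ASADE and USADE "constitute adverse events where relationship to investigational device or study procedure is indicated".

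**Tabulation.** Protocol 9.2.3.2 states: "The descriptive tables will be presented with respect to intensity, seriousness, and relationship to the treatment". SAP 7.10.2 plans one breakdown by causality, in the overview and again by system organ class and preferred term. Neither document plans separate device and procedure tables, and neither defines a procedure. The visit lists in protocol 3.5 even count self-administration of the pessary among the procedures performed.

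**The concern.** The scale asks one question at its two ends and another in its middle, and its result is then labelled as relationship to treatment. An event that an investigator firmly attributes to a speculum or swab meets the wording of the highest level, and the planned tables give no way to see that the pessary was not the suspected cause.

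This matters here for three reasons. Safety and tolerability form a co-primary endpoint, and tolerability is judged from adverse events alone. The pessary has not been tested clinically before. The trial has one arm, so no control group shows the background rate of local events from examination and sampling, which act on the same site as the product. Attribution rests on this scale.

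**Working it through.** The plan states no figure to reproduce on this point. The check sets the passages side by side, traces one event through them, and then gives the effect of one patient on the tables.

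**Step 1. What each passage refers to**

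| Place | Relationship to |
|---|---|
| Protocol 7.5.2, instruction to the investigator | device |
| 7.5.2 *Not Related* | device or procedures (to be excluded) |
| 7.5.2 *Unlikely* | device |
| 7.5.2 *Possible* | device |
| 7.5.2 *Probable* | device |
| 7.5.2 *Causal Relationship* | device or procedures |
| Protocol 7.3, running text on ADE | use of the device |
| Protocol 7.3, Table 4 | device or procedure |
| SAP 7.10.2, ISO terms | device or study procedure |
| Protocol 9.2.3.2, tables | treatment |

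**Step 2. Trace one event.** Take local discomfort that the investigator firmly attributes to the Day 7 swab.

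- Following the instruction (device only), the investigator looks for a low level. *Not Related* is blocked as worded, because a link to procedures cannot be excluded. *Unlikely* fits, since another cause explains the event.
- Following the definition of the top level, the event is associated with a procedure beyond reasonable doubt, so *Causal Relationship* fits. That level's list includes ruling out other causes, but 7.5.2 adds that not every criterion need be met together.

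The same event can thus be placed at the second-lowest or the highest of five levels, each time with support in the text. If it is placed at the highest, protocol 9.2.3.2 shows it as related to treatment.

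**Step 3. Which occasions are exposed.** SAP 7.10.2 tabulates only events that start after the first dose, and SAP 7.1.2 puts that dose after the Day 0 visit. An event from the Day 0 examination or swab therefore enters the tables only if it starts after that dose. The main exposed occasions are:

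- Day 7 examination and swab: all patients
- Day 14 examination and swab: patients on prolonged treatment
- Day 35 self-swab (no prolonged treatment) or Day 42 self-swab (prolonged treatment). These fall at the last contact, so under protocol 7.6 an event from them is captured only if it is known by then.

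**Step 4. Size per patient.** The planned number treated is 24 (SAP 5). If all receive at least one dose, the full analysis set has 24 patients. A patient whose only related event is procedural changes the proportion with a related event by

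1/24 = 0.0417, or 4.2 percentage points.

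The documents give no rate for procedure-related events, so the number of such patients cannot be stated.

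**The case against.** The case on the other side is substantial, and much of it stands.

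- *ADE classification has a governing rule.* Protocol 7.3 says the categorization follows Table 4, and the SAP agrees with it. A reader might infer that an ADE rate within the co-primary endpoint changes with the passage applied. The documents do not support that: SAP 7.10.2 lists no ADE count or rate, and uses the ISO terms only in an explanatory sentence. The effect is on the causality tables.
- *The scale permits the wrong rating but does not force it.* A reader might infer that a swab event must be rated *Causal Relationship*, or that one only probably due to a swab has no level. Neither follows. The instruction is device-only, and *Unlikely* can hold an event that another cause explains.
- *Exposure is limited.* Counting every examination, two or three per patient, would overstate it, because the Day 0 examination comes before the first dose. The protocol's risk section also expects no major inconvenience from sampling.
- *No event is hidden.* All treatment-emergent events are tabulated by system organ class and preferred term whatever their cause, and patient listings are planned. Safety has no hypothesis test. Counting procedural events as related errs on the cautious side for a new product.
- *The eCRF and Data Display Plan are not among the documents.* They may already separate the two relationships.

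What does not stand is the view that this is only untidy wording. A stated rule lets an event be reported as treatment-related when the rater holds that the treatment did not cause it. The cautious direction is not assured either, because a rater who follows the instruction would place the same event low.

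**Conclusion.** The point holds for the causality tables. Protocol 7.5.2 is internally inconsistent, and an event clearly caused by an examination or swab can be rated at its top level and then shown as related to treatment in a single breakdown. The mismatch between the 7.3 running text and Table 4 is real but secondary, since Table 4 governs.

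Each affected patient moves the related-event proportion by 4.2 points, assuming 24 treated patients and no other related event in that patient. How many patients would be affected is unknown. The endpoint is descriptive, so no test, error rate or sample size is touched. The conclusion also assumes that the eCRF and Data Display Plan do not already separate the two relationships; if they do, only the wording and the table layout need to change.

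**What to change.** 1. In protocol 7.5.2, apply all five levels twice: once to the device, including applicator and insertion, and once to study procedures, defined as examination and swabs.
2. In SAP 7.10.2 and protocol 9.2.3.2, tabulate the two relationships separately. Keep a combined device-or-procedure line so that the Table 4 categories can still be reported.
3. Align the running text of protocol 7.3 with Table 4.

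The cost is wording in both documents, one more table split, and one extra causality question per adverse event if the eCRF does not already record both. The protocol planned the last visit for February 2019, and the final SAP is dated January 2020. If that timetable held, the second rating would have to be made retrospectively from recorded events, and the report should say so.
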